Inclusion criteria will be a diagnosis of narcolepsy type 2 or idiopathic hypersomnia. These diagnoses will be made in accordance with the International Classification of Sleep Disorders, third edition (ICSD-3) criteria (24). All participants will have daily sleepiness for at least three months and an absence of cataplexy. For patients in whom hypocretin has been tested, values will be above 110 pg/mL. Participants with narcolepsy type 2 will additionally demonstrate a multiple sleep latency test mean sleep latency (MSLT-SL) less than or equal to 10 minutes, with at least two sleep onset REM periods (SOREMs) between nocturnal polysomnogram and next-day MSLT. Participants with idiopathic hypersomnia will demonstrate at least one of: 1) MSLT-SL less than or equal to 10 minutes, with fewer than two sleep onset REM periods (SOREMs) between nocturnal polysomnogram and next-day MSLT; 2) total sleep time of > 660 minutes accrued over up to 24 hours of continuous polysomnographic monitoring; or 3) 24-hour total sleep time of > 660 minutes, as estimated by wrist actigraphy averaged over at least 7 days.

Participants suspected of having a diagnosis of narcolepsy type 2 or idiopathic hypersomnia who have never had a nocturnal polysomnogram and next-day MSLT, will be scheduled for an additional study visit to complete an overnight and day study prior to visit 2.

Participants already diagnosed with narcolepsy type 2 or idiopathic hypersomnia must be free of wake-promoting medication or willing to discontinue current wake-promoting medication. Medicines will be discontinued for up to two weeks; length of discontinuation will be dependent on the half-life of the medication(s).

During the research slow-down created by the COVID19 pandemic, several modifications will be made to allow continued data collection while protecting the health of participants, study staff, and the population:

1) Consent and questionnaires will be completed virtually, rather than in-person. The video platform that will be used to complete virtual consents and questionnaires is Zoom. This platform is currently approved by Emory.

- 2) Investigational drug will be shipped directly to the participant from IDS, rather than having the participant pick up in person from IDS

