Intention-to-treat analyses will be performed, using last observation carried forward in the event of participant drop-out. The change in ESS at week 12 from baseline will be compared between the two treatment groups via t-test (compared for unequal variances if necessary) and will be evaluated on a hypothesis of non-inferiority. Similar analyses will be performed on secondary outcomes, considering the proportion of responders in each treatment arm who rate themselves "much improved" or "very much improved". Categorical outcomes, including these PGI-C proportions and adverse events, will be compared using Chisquare or Fisher exact test. Exploratory analyses will evaluate response at week 4 and week 8 between the two medications groups, to determine if there is a difference in time to symptom control.

Considering each medication separately, predictors of response will be assessed using logistic regression. The main predictor of interest will be hypersomnia diagnosis, i.e., narcolepsy type 2 or idiopathic hypersomnia. Other predictors, to be considered in separate, exploratory regression models, include: MSLT mean sleep latency, MSLT number of SOREMs, sex/gender, baseline ESS, age, and comorbidities. Significant predictors in univariate models will be combined in a multivariate model. Although the investigative team has extensive clinical trial and statistical experience, additional statistical consultation will be provided as needed through Emory's CTSA consultation program.

Data Safety Monitoring and Reporting

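### Aim 3 builds its final model from univariate significance in arms of 22, with no error control, and can put SOREM count into the same model as the diagnosis it largely defines

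*Combined protocol and SAP*

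**What the plan says.** The Statistical Analysis section sets the unit of analysis: "Considering each medication separately, predictors of response will be assessed using logistic regression". It then names one lead variable: "The main predictor of interest will be hypersomnia diagnosis, i.e., narcolepsy type 2 or idiopathic hypersomnia". Six further candidates are listed, "MSLT mean sleep latency, MSLT number of SOREMs, sex/gender, baseline ESS, age, and comorbidities", and these are "to be considered in separate, exploratory regression models". The last step is the selection rule: "Significant predictors in univariate models will be combined in a multivariate model".

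The section gives no significance level, test, multiplicity adjustment, limit on model size, rule for overlapping predictors or validation step for this rule. Aim 3 has no sample size or power statement of its own.

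The inclusion criteria in Study Design & Methods define the two diagnoses partly by SOREM count. Narcolepsy type 2 is entered "with at least two sleep onset REM periods (SOREMs) between nocturnal polysomnogram and next-day MSLT". The first route to idiopathic hypersomnia is "with fewer than two sleep onset REM periods (SOREMs) between nocturnal polysomnogram and next-day MSLT". Both carry the same 10-minute ceiling on mean sleep latency. The other two routes to idiopathic hypersomnia rest on long sleep time and set no SOREM limit. While the sleep laboratory is closed for COVID-19, a provisional diagnosis needs no MSLT.

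**The concern.** There are two separate weaknesses. First, letting univariate p-values decide what enters the model favours chance findings when many candidates are tested in a small arm. Second, SOREM count is a candidate alongside diagnosis, although it largely determines diagnosis. If diagnosis predicts response, SOREM count tends to pass the screen with it. The rule then adjusts the main predictor for something close to its own definition.

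Aim 3 is meant to help clinicians and patients choose between the two drugs. At stake is whether the reported predictors are real, and whether a real diagnosis effect stays legible in the model that readers will take as final.

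**Working it through.** **Inputs from the plan.** 22 per arm; two arms analysed separately; diagnosis plus six listed candidates, so at least 7 per arm and 14 in all (comorbidities may be several variables); planned response 80%.

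**Assumptions.** A two-sided 5% level per test. The 25% ESS reduction, stated for non-inferiority, is also the Aim 3 response. SOREM, latency, covariate and case-mix distributions are assumed.

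**The plan's own figure.** The responder sample size supplies the event count. With 80% response, a 30-point margin, 80% power and one-sided 5%: n = (1.645 + 0.842)² × 2 × 0.8 × 0.2 / 0.3² = 6.18 × 3.556 ≈ 22 per arm. It reproduces. It implies 22 × 0.2 = 4.4 non-responders per arm, or 4.4 / 7 ≈ 0.6 per candidate. At 50% response it would be 11 / 7 ≈ 1.6.

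**False hits, nominal (independent tests).**
- At least one in an arm: 1 − 0.95⁷ = 30.2%.
- At least one over both arms: 1 − 0.95¹⁴ = 51.2%.
- Two or more in one arm: 1 − 0.95⁷ − 7 × 0.05 × 0.95⁶ = 1 − 0.698 − 0.257 ≈ 4.4%.
- If diagnosis is kept outside the screen, six tests give 26.5% per arm and 46.0% over both.

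**False hits, simulated.** 3,000 runs per scenario, no true predictor, 40% with narcolepsy type 2. The two-arm figure is 1 − (1 − per-arm rate)².

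| Response | LR, per arm | LR, both arms | Wald, per arm | Wald, both arms |
|---|---|---|---|---|
| 80% | 38% | 62% | 7% | 14% |
| 60% | 35% | 58% | 16% | 30% |
| 50% | 35% | 57% | 18% | 33% |

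A second simulation, at 60% and 80% response, gave 59–62% over both arms with likelihood-ratio (LR) tests. Two or more hits in the same arm occurred in 8–10% of arms with LR tests and 1–3% with Wald tests. Wald tests are conservative here because there are so few non-responders.

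**Overlap of SOREM count and diagnosis.** The simulated correlation was about 0.86. In a linear approximation the variance inflation is 1 / (1 − 0.86²) = 3.84, and √3.84 ≈ 1.96, so the standard error for diagnosis roughly doubles. Other assumed SOREM distributions gave correlations of 0.82–0.88 (variance inflation 3.0–4.4). The correlation between diagnosis and latency was only about −0.38.

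**Diagnosis as the only true predictor (per arm).** The response rates correspond to odds ratios of 6, 13.5 and 9.3, for example (0.9/0.1) / (0.6/0.4) = 6.

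| Response in the two diagnoses | Test | Diagnosis passes | Both pass | SOREM passes, given diagnosis passes |
|---|---|---|---|---|
| 60% vs 90% | LR | 44% | 27% | 60% |
| 60% vs 90% | Wald | 16% | 8% | 48% |
| 40% vs 90% | LR | 76% | 57% | 76% |
| 40% vs 90% | Wald | 43% | 25% | 59% |
| 30% vs 80% | LR | 69% | 55% | 79% |
| 30% vs 80% | Wald | 55% | 35% | 63% |

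With a true odds ratio of 3, both pass in only 14–17% of arms (LR) or 2–8% (Wald). Once both are in the joint model, neither is significant in 67–85% of cases across the simulations with LR tests, and in 95–99% with Wald tests.

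**The case against.** The strongest defence is that this is the third aim, that diagnosis is singled out in advance, and that the other predictors are already called exploratory. On a fair reading the single-predictor diagnosis result would be reported before any combined model, so a later unstable model would not erase it. That stands as a limit on the harm. It does not remove the fault: the exploratory label belongs to the separate models, not to the combined one, and the plan does not say which model carries the Aim 3 conclusion.

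Four stronger readings are tempting, and the documents do not support them.
- **Sleep latency is also a recoding of diagnosis.** It is not. The 10-minute cut is the same for both diagnoses, so it does not separate them.
- **The final model will often hold false predictors.** The large percentages count any single hit over two arms. A model combining two or more false predictors arises in about 1–10% of arms when nothing is predictive, and the rate depends on a test that the plan does not name.
- **Neither effect can be estimated jointly.** A roughly doubled standard error means imprecision, not inestimability.
- **SOREM count is a complete duplicate.** The long-sleep routes carry no SOREM limit, and participants enrolled without an MSLT may have no count, so the overlap is weaker for them.

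**Conclusion.** The concern holds in a limited form. The selection rule has no error control. With no true predictor, at least one false hit over both arms is expected in about 51% of trials nominally, 57–62% with likelihood-ratio tests and 14–33% with Wald tests. That the plan's error rate cannot be fixed more closely is itself a consequence of stating neither level nor test.

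The overlap problem is conditional. If diagnosis truly matters and passes, SOREM count follows in roughly half to four fifths of cases (48–79%), and the joint model then usually shows neither as significant. These figures rest on the assumed 5% level, the assumed response definition and the assumed SOREM distributions, and the 48–79% on large true effects. That SOREM count helps to define diagnosis rests on the inclusion criteria alone.

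A reader might infer that the trial's main comparison is compromised. It is not: the primary, secondary and safety comparisons do not use this rule. The point should be corrected, but it concerns Aim 3 only.

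**What to change.** Replace the selection sentence in the Statistical Analysis section with text to this effect:
- The pre-specified Aim 3 analysis in each arm is the logistic model with diagnosis as the only predictor.
- Every other listed predictor is reported from its own single-predictor model, with its estimate and 95% confidence interval whatever the p-value, and labelled exploratory. No combined model is built from significant results.
- SOREM count is never entered in the same model as diagnosis. Sleep latency needs no such bar.

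If an adjusted model (diagnosis plus baseline ESS) is wanted, specify it in advance and use Firth-penalised logistic regression, or analyse continuous ESS change. With about 4.4 non-responders expected per arm, an ordinary two-predictor logistic model is itself thin.

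With diagnosis as the only tested predictor, the nominal false-positive chance falls from 30.2% to 5% per arm, and from 51.2% to 1 − 0.95² = 9.75% over both arms. The cost is about two sentences of text and the loss of a multi-predictor final model, which 22 people per arm can hardly support. No extra data or participants are needed. The diagnosis estimate will still be imprecise, and its interval should be shown as such.

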Aim 1: To compare the effectiveness of modafinil and amphetamine salts in patients with narcolepsy type 2 or idiopathic hypersomnia. The primary outcome will be the change in Epworth Sleepiness Scale score from pre-treatment baseline. Secondary outcomes will include Patient Global Impression of Change from baseline for sleepiness, sleep inertia, and cognitive dysfunction.

Aim 2: To compare the safety of modafinil and amphetamine salts in the treatment of narcolepsy type 2 or idiopathic hypersomnia.

Aim 3: To evaluate for clinical predictors of response to modafinil and amphetamine salts in these patients.

Study Design & Methods

Treatment-naïve adult patients (n = 44), or adult patients free of wake-promoting medication or willing to discontinue current wake-promoting medication seeking evaluation at the Emory Sleep Center for narcolepsy type 2 or idiopathic hypersomnia will be invited to participate and randomized to one of the treatment arms upon consent. Although pragmatic trials often do not involve blinding to condition, those trials where outcomes of interest are primarily subjective often require blinding to minimize bias (20), which will be necessary in this case. Randomization, allocation concealment, blinding, and medication dispensing will be managed by Emory's Investigational Drug Service (IDS). The IDS will use 1:1 computer generated randomization (23), with a block design to ensure equal number of participants receiving each study medication. Block size will not be disclosed to the study investigators or staff. Identity of medications will be concealed by the pharmacy using matched pills and pill containers. The IDS is located in a separate building from the study team and will have no interaction with participants. Medications will be transferred from the pharmacy via courier. This protocol will be approved by the Emory University Institutional Review Board and registered at clinicaltrials.gov prior to enrollment of the first participant.

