- 3) Inclusion criteria will be changed to eliminate the need for PSG/MSLT. The Emory sleep lab is currently closed for non-urgent procedures, and so no patients suspected of having idiopathic hypersomnia or narcolepsy can currently undergo PSG/MSLT. We will use the following for the provisional diagnosis of idiopathic hypersomnia or narcolepsy type 2 during the period that the sleep lab is closed for testing:
 - a. Clinical suspicion of idiopathic hypersomnia or narcolepsy type 2 by a sleep medicine provider
 - b. Home sleep apnea test demonstrating absence of obstructive sleep apnea (pAHI < 15), if sleep medicine provider feels that a home sleep apnea test is clinically indicated to rule out sleep apnea
 - c. Sleep diary x 1 week demonstrating average sleep time > 7 hours/night and no individual nights of < 6 hours
 - d. Other inclusion/exclusion criteria will continue to apply

Exclusion criteria will include obstructive sleep apnea (AHI > 15), severe periodic limb movements of sleep with arousals (PLM arousal index > 30), allergy to either of the study drugs, and contraindication to either of the study drugs. For modafinil, these contraindications include: history of left ventricular hypertrophy, mitral valve prolapse, severe cardiovascular disease, unstable angina, myocardial infarction, severe hepatic impairment, substance abuse history, psychosis, or unstable depression or mania (25). Contraindications to amphetamine salts, in addition to those listed above, include: other cardiac structural abnormalities, cardiomyopathy, severe arrhythmias, uncontrolled hypertension, glaucoma, Tourette's syndrome, and epilepsy. Women who are pregnant, planning to become pregnant within 16 weeks, or breastfeeding will be excluded, as the safety of these medications during pregnancy and breastfeeding is not well-established. Participants who have taken either modafinil or amphetamine salts for another indication (e.g., ADHD) will be excluded if it has been < 12 months since this treatment.

Participants who are taking a medication that has a potential interaction with modafinil to cause QTc prolongation will be eligible if either: 1) they can safely discontinue the potentially interacting medication prior to and throughout the study (in conversation with the prescribing physician), or 2) they undergo an an electrocardiogram (EKG) prior to baseline visits that shows a normal QTc interval while on the potentially interacting medication.

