Medications will be provided initially as: modafinil 100 mg qam and amphetamine salts 10 mg qam. For patients reporting difficulty awakening at baseline, the first dose will be taken 1 hour before planned awakening, whenever possible. For patients without difficulty awakening at baseline, first dose will be taken upon awakening. Patients will be advised to increase dosage once a week with the following schedule: week 2, 1 pill qam and 1 qnoon; week 3: 2 pills qam and 1 qnoon; week 4 and beyond: 2 pills qam and 2 pills qnoon. Patients will be instructed not to titrate further once they feel symptoms are well-controlled and to reduce dosage one step in the case of mild to moderate side effects. In the case of severe side effects, participants will be instructed to discontinue treatment but will still continue all remaining study visits and questionnaires. This titration will allow participants to reach doses of modafinil as high as 200 mg bid, the maximum FDA approved dose of modafinil in the treatment of narcolepsy. Participants will reach a maximum dose of amphetamine salts of 20 mg bid. Although the maximum FDA approved dose of amphetamine salts for treatment of narcolepsy is higher at 60 mg/day, adverse events are dose-related and higher doses do not necessarily convey additional benefit (33); in clinical practice, finding the lowest effective amphetamine dosage and maintaining this dosage as long as it is effective is a practical component of the management of both the risk of side effects and the problem of tolerance that occurs in 1/3rd patient with narcolepsy treated with amphetamines (34).

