This study will recruit up to 55 participants, with a sample size target of 44 participants who complete participation in the 12 week medication trial. Participants will be newly diagnosed, medication-naïve individuals, or formerly diagnosed, free of wake-promoting medication or willing to discontinue current wake-promoting medication with diagnoses of: narcolepsy type 2 or idiopathic hypersomnia.

Inclusion criteria will be: 1) narcolepsy type 2 or idiopathic hypersomnia; 2) age 18-65; 3) informed consent.

Exclusion criteria will be: 1) contraindication to modafinil or amphetamine salts (history of left ventricular hypertrophy, mitral valve prolapse, other cardiac structural abnormalities, severe cardiovascular disease, unstable angina, myocardial infarction, cardiomyopathy, severe arrhythmias, uncontrolled hypertension, severe hepatic impairment, substance abuse history, psychosis, glaucoma, Tourette's syndrome, and epilepsy); 2) obstructive sleep apnea (AHI > 15); 3) severe periodic limb movements of sleep with arousals (PLM arousal index > 30); 4) allergy to either of the study drugs; and 4) pregnancy or breastfeeding.

Participants who withdraw from study medication will be invited to complete remaining questionnaires/study visits.

Visit Schedule

Visit 1: Enrollment: After reviewing information about the study and confirming participation, subjects will answer questions about their sleep disorder and the symptoms experienced. This visit is expected to last about one hour. If participants are suspected of having a diagnosis of narcolepsy type 2 or idiopathic hypersomnia and have never had an overnight polysomnogram (PSG) and next-day MSLT, they will be scheduled for an

additional study visit to complete a PSG and MSLT before visit 3. If participants already have a confirmed diagnosis of narcolepsy type 2 or idiopathic hypersomnia and are taking certain stimulant medications they will be asked to wean off of this medication before and during the study. After weaning off of medicines, the participant will be given a four-week supply of one of the two study medications. The medication will be provided will be assigned randomly, the participant and the doctor will not be told which of the two study medications are given.

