Visit 2: Participants will only participate in this visit if they haven't had a sleep study prior to enrollment. Sleep testing: During this visit, participants will come to the Sleep Center for an overnight sleep study, during which they will be monitored with multiple wires on their body to measure sleep, breathing, and activity at night. The next day, they will remain at the Sleep Center until approximately 5 pm, taking naps five times during the day.

After these results are received and if the results are positive for a diagnosis of narcolepsy type 2 or idiopathic hypersomnia, participants will be given a four-week supply of one of the two study medications and will proceed with the remaining study visits. If the results are negative for narcolepsy type 2 or idiopathic hypersomnia, participants will be withdrawn from the study.

Visit 3 (four weeks medication dispensed at either Visit 1 or Visit 2): Complete questionnaires and pick up medication for the next four weeks (the same medication they have been taking already) at the Emory Sleep Center.

Visit 4 (four weeks after Visit 3): Complete questionnaires and pick up medication for the next four weeks (the same medication they have been taking already) at the Emory Sleep Center.

Visit 5 (four weeks after Visit 4): Meet with a study team member to discuss experience with the medication. Complete questionnaires and return any unused study drug.

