Participants will be screened for medication contraindications (detailed above) prior to participation, to minimize risk of serious drug adverse reactions. During the study, participants will be encouraged to report any adverse events and will be provided with 24-hour contact information with which to do so. Participants will be systematically assessed for expected and idiosyncratic adverse reactions every four weeks during participation. [name] will review routine adverse event logs at least once a week. For adverse events reported between routine assessments, [name] or [name] will review immediately and provide guidance to the participant on if and how to adjust study mediation (e.g., discontinue in the case of a severe adverse reaction) and any additional care that should be sought (e.g., urgent or emergency care). [name] will convey any reportable events to the Emory IRB using the standard reporting timeline, based on event severity. [name] will also oversee protocol compliance and data accuracy. She will perform reviews of case report forms every four weeks, to ensure consistency with protocol and data entry accuracy. [name] and the study coordinator will work together to complete the Emory IRB's "EU Self-Monitoring Tool" (available at http://www.ctac.emory.edu/clinical_trial_guidebook/data_and_safety_monitoring_plans.html) every six months.

Confidentiality

Data collection will be performed using the REDCap research tool, including online assessments. REDcap provides secure, web-based applications that offer easy data manipulation with audit trails for reporting, monitoring, and querying patient records and an export mechanism to statistical programs (e.g., SAS). REDcap servers are housed in a local data center at Emory University and all web-based information transmission is encrypted. REDcap was developed specifically to be compliant with HIPAA-security guidelines. Paper records (e.g., consent forms) will be stored in a locked office. When subsets of data are

housed on individual computers for data analysis and manuscript preparation, the minimum amount of identifiers will be included and computers will be encrypted.

Citations

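### The protocol specifies no blood pressure or heart rate reading at any visit, although uncontrolled hypertension is an exclusion and hypertension and tachycardia are listed drug risks

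*Combined protocol and SAP*

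**What the plan says.** Data Safety Monitoring and Reporting states: "Participants will be screened for medication contraindications (detailed above) prior to participation, to minimize risk of serious drug adverse reactions". Study Design & Methods places raised blood pressure among the amphetamine-specific items: "Contraindications to amphetamine salts, in addition to those listed above, include: other cardiac structural abnormalities, cardiomyopathy, severe arrhythmias, uncontrolled hypertension". Participant Selection then makes it an exclusion for everyone ("severe arrhythmias, uncontrolled hypertension, severe hepatic impairment"), which is logical because either drug may be assigned: "The IDS will use 1:1 computer generated randomization". Neither place gives a threshold or a method of assessment.

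The adverse event list in Study Design & Methods covers both drugs together. It puts palpitations/tachycardia among the common events, and HTN among both the less common and the rare but serious ones.

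Dosing starts at one pill a day and rises weekly, ending with "week 4 and beyond: 2 pills qam and 2 pills qnoon". Participants stop increasing when they feel their symptoms are well controlled, are told to "reduce dosage one step in the case of mild to moderate side effects", and stop treatment if side effects are severe. The Visit Schedule times the next contact as "Visit 3 (four weeks medication dispensed at either Visit 1 or Visit 2").

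On treatment, the safety section provides an adverse reaction assessment every four weeks, at least weekly review of the event log, and a 24-hour contact. It names no measurement.

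**The concern.** The plan relies on an exclusion that it gives no means of applying to someone who does not know that their blood pressure is high. Hypertension is often silent, so history alone cannot show that pressure is controlled on the day of entry. On treatment, every rule that stops or lowers the dose depends on what the participant feels or reports, so a symptomless rise in pressure or pulse triggers nothing. At stake is the safety of an unrecognised hypertensive participant allocated to amphetamine salts. A secondary consequence is that Aim 2, the safety comparison, has no specified cardiovascular measurement behind it, only reported events.

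**Working it through.** The plan states no figure on this point, so the check is a reading of each relevant part, followed by a dose timeline.

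**1. Where a reading could be specified**

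- *Appendix 1, all 21 rows.* There is no row for vital signs, blood pressure, heart rate, physical examination or EKG. The rows that bear on eligibility or safety are Medical History and Study Inclusion/Exclusion (Visit 1), Concomitant Medication Review (Visits 1 to 5) and Adverse Experiences (Visits 2 to 5).
- *Visit Schedule.* The five visits consist of questions and questionnaires, sleep testing where needed, weaning, drug supply and return, and a closing discussion. No reading is mentioned.
- *Data Safety Monitoring and Reporting.* It covers screening and periodic assessment, without a measurement.
- *Study Design & Methods.* The only cardiac test is an EKG before baseline, read for QTc, as one of two routes to eligibility for people taking a QTc-interacting drug. The Visit 2 sleep study is described as recording sleep, breathing and activity. It applies only to those without a previous study and comes before dosing.

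Result: a blood pressure or heart rate reading is specified at 0 of 5 visits.

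**2. Whether the exclusion can be applied as written**

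Other criteria have cut-offs: AHI above 15, PLM arousal index above 30, hypocretin above 110 pg/mL where tested, and MSLT latency of at most 10 minutes. Uncontrolled hypertension has none, so two assessors could apply it differently.

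**3. Dose steps against visits**

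Inputs: 10 mg amphetamine salts per pill and the weekly steps, from Study Design & Methods; Visit 3 about four weeks after dispensing, from the Visit Schedule. Assumption: the first dose is taken at about the time of dispensing. Week k starts on day 7(k − 1) + 1.

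| Week | Starts about day | Pills per day | Amphetamine salts per day |
|---|---|---|---|
| 1 | 1 | 1 | 10 mg |
| 2 | 8 | 1 + 1 = 2 | 20 mg |
| 3 | 15 | 2 + 1 = 3 | 30 mg |
| 4 onward | 22 | 2 + 2 = 4 | 40 mg |

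Visit 3 falls at about day 28, roughly 28 − 22 = 6 days after the last step. All three scheduled increases therefore come before the first scheduled on-treatment visit. Appendix 1 marks the titration review at Visit 1 only.

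**4. What the specified safeguards can detect**

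| Situation | Specified means of detection |
|---|---|
| Known or treated hypertension at entry | Medical History, Study Inclusion/Exclusion, Concomitant Medication Review |
| Unrecognised hypertension at entry | None |
| Symptomatic rise on treatment | Step-down rule, 24-hour contact, log review, four-weekly assessment |
| Silent rise on treatment | None |

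**The case against.** The strongest reply is that the plan already has means of applying its exclusions. Known hypertension should surface in the Visit 1 history and eligibility check, or through antihypertensive drugs at the medication review. The COVID-19 changes (item 3d) keep the remaining criteria in force. The amphetamine dose is capped at 40 mg/day, below the 60 mg/day maximum that the protocol cites, and participants stop titrating once they feel well controlled. This is also a pragmatic trial at a sleep clinic, where blood pressure may be taken routinely. All of this stands, and it narrows the gap to unrecognised hypertension and silent rises. It does not close it, because none of these safeguards requires a reading. Routine clinic contact is also least dependable in the remote period, when consent and questionnaires are virtual and drug is shipped.

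Three stronger readings are tempting and are not supported:

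- *That no reading is taken or recorded.* The case report forms and the Visit 1 Sleepy Packet are not in the documents. What can be said is that the protocol specifies none.
- *That the hypertension and tachycardia risks are shown for modafinil too.* The adverse event list is pooled and attributes no item to either drug.
- *That every amphetamine participant reaches 40 mg/day.* The schedule permits up to three increases; it does not impose them.

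**Conclusion.** The concern holds as an omission in the protocol: no reading at any of five visits, no threshold for the exclusion, and up to three dose increases before the first scheduled on-treatment visit. Followed as written, the plan could enrol a participant with unrecognised uncontrolled hypertension, allocate amphetamine salts, and not detect the problem unless symptoms appeared. Confidence in this is high, subject to the assumption that the first dose is taken close to dispensing.

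A reader might go on to infer how many people would be affected. The documents do not support any figure: they give no prevalence of unrecognised hypertension and no threshold. Nor is the number dosed fixed by the recruitment ceiling. Outside the remote period some recruits leave before treatment ("If the results are negative for narcolepsy type 2 or idiopathic hypersomnia, participants will be withdrawn from the study"), but that filter does not operate while the sleep laboratory is closed.

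A reader might also infer that measured readings would make Aim 2 decisive. With 22 per arm they would add useful description and little more. The case rests on participant safety. The change should be made, but it is not a condition for a valid efficacy result.

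**What to change.** 1. Add a row for blood pressure and heart rate to Appendix 1: a seated reading at Visit 1 before eligibility is confirmed, and readings at Visits 3, 4 and 5. For participants who wean off a wake-promoting drug, repeat the reading after washout and before dispensing, and use that one as baseline.
2. In Study Design & Methods and Participant Selection, define uncontrolled hypertension by a mmHg threshold set by the study physicians. The documents offer no value.
3. Add to the titration rules, identically for both blinded arms: if a repeated reading is at or above a physician-set limit, hold the dose or step down one level and contact the study physician. Set the pressure and pulse limits separately.
4. In the remote period, accept a recent clinic or home-cuff reading and record its source. The same can serve at weeks 4 and 8 if those contacts are remote, as Study Design & Methods says, and not clinic pick-ups, as the Visit Schedule says.
5. Report change from baseline by arm under Aim 2, descriptively.

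A cuff reading before the final dose step is optional. It would check the 30 mg/day level, but it falls between visits and would need arranging. If only part is feasible, items 1 and 2 come first.

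Cost: a few minutes per visit with standard equipment, some case report form fields and no new staff. Downsides: home readings will be less standardised and sometimes missing, one brief extra contact may be needed after washout, a few candidates may be excluded, and there is a small risk that readings hint at the allocation.
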